## Study Protocol

### **Purpose**

The purpose of the current study is to test whether sending email communications in a timely manner - when patients have laboratory results available to view on the myGeisinger patient portal - increases enrollment in the portal. Secondly, this study A/B tested 2 different versions of the timely email.

### **Method**

#### *Sample*

The study population consisted of patients aged 18 or older who were not yet enrolled in myGeisinger, who had an email address on file, for whom a lab or test was ordered within 30 days prior to the email date, and whose lab or test result was released to myGeisinger the day before the email date. Patients who had declined enrollment in myGeisinger were excluded from the study.

Based on the above criteria, N = 5,012 patients were randomized to a study condition and sent an email between May 18, 2020 and June 1, 2020 (15 days). Patients who had multiple lab/test results in this period were only randomized to a study condition once, upon their first qualifying result, and did not receive more than one email. Electronic Health Records (EHR) for study patients were subsequently examined to evaluate portal enrollment; records for 3 patients were no longer present in the EHR, leaving a total of N = 5,009 patients for analysis. All comparisons between patients emailed and those not contacted were conducted within this total.

Within the analyzed sample, 3,340 patients were allocated to an email condition. Of these, 404 were flagged by the email delivery software as invalid email addresses and were thus not sent an email. Subsequently, an additional 186 emails bounced, leaving a total of N = 2,750 emails delivered. All comparisons between the two email conditions were conducted within this total.

#### *Intervention*

Patients were randomly assigned to one of three conditions, two of which entailed an email. Each intervention is named and described in the pre-registration under "Groups and Interventions."

#### *Outcomes Timeframe*

As described in the "Outcome Measures" section of the pre-registration, we examined study outcomes within one week (or 7 days) after they received the intervention (for the patients in the email groups) or, for the control group, within one week after they would have received the intervention had they been in an email group. For example, if the patient was emailed on 5/20/20, we assessed if they had enrolled by 5/26/20. Secondary analyses examined study outcomes within one month (or 31 days) after the intervention.

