## Statistical Analysis Plan

The primary question of interest was whether a timely email improves one-week patient portal enrollment when compared with no such email. This was evaluated using a logistic regression (a generalized linear model with a binary distribution and log-link function) in an intent-to-treat design: patients who were randomized to receive an email but whose addresses were scrubbed by the email delivery software were still included in any such comparisons with the control group, so the total sample size was  $N = 5,099$ .

A secondary question of interest was whether one email version performed better than the other. This question was assessed by examining whether a patient opened the email, clicked on the registration link in the email, unsubscribed from email communications, or enrolled within the outcome timeframe (1 week). This was evaluated for all four outcome measures using a logistic regression (a generalized linear model with a binary distribution and log-link function). These analyses focused on patients' responses to the two email conditions and thus only included patients who were successfully sent the email,  $N = 2,075$ . Unsubscribe data was unexpectedly unavailable at 1-week post-intervention, so this measure was collected and analyzed at 1-month post-intervention instead.

Finally, for the primary question of interest, a secondary analysis was conducted 1 month (31 days) after the intervention.

For all tests, odds ratios (ORs) were calculated, along with 95% confidence intervals (CIs); two-tailed p-values  $< 0.05$  were used to determine statistical significance.

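### Does the one-week outcome window close six or seven days after the email, and does the difference matter?

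*Combined protocol and SAP*

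**What the plan says.** The Outcomes Timeframe section of the protocol gives the window for emailed patients as "within one week (or 7 days) after they received the intervention". Controls get a matching window, "within one week after they would have received the intervention had they been in an email group". An illustration follows directly: "if the patient was emailed on 5/20/20, we assessed if they had enrolled by 5/26/20". For the longer follow-up the section says "Secondary analyses examined study outcomes within one month (or 31 days) after the intervention" and gives no dated example. It also refers the reader to the outcome measures in the pre-registration, which is not among the documents.

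The Statistical Analysis Plan applies the one-week window to the primary question, "whether a timely email improves one-week patient portal enrollment when compared with no such email", and to enrolment in the comparison of the two email versions. Neither the protocol nor the SAP says whether the email date is day 0 or day 1.

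**The concern.** Read literally, the rule and its example disagree by one day. An analyst who codes the rule keeps enrolments with enrolment date minus email date of at most 7. An analyst who codes the example uses at most 6. The two differ on every patient who enrolled exactly seven days after the email date. Because this variable is the primary endpoint, two people working from the same text could report different event counts.

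Two further worries attach to the shorter window. It might lose real events. It might also count people who enrolled on the email date before the message went out, which would add equal noise to all arms and pull the odds ratio toward 1. The 31-day window could carry the same ambiguity.

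**Working it through.** **Inputs.** Outcomes Timeframe: email date 5/20/20, cutoff 5/26/20, windows of 7 and 31 days. Sample: email period May 18 to June 1, 2020, stated as 15 days.

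**Step 1: reproduce the example's cutoff.**
- Literal count (email date is day 0): 5/20 + 7 days = 5/27. This does not give 5/26.
- Inclusive count (email date is day 1): 5/20 + 6 days = 5/26. This does.
- Elapsed days: 26 − 20 = 6. Calendar dates with both ends counted: 6 + 1 = 7.

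**Step 2: see how the document counts elsewhere.** From May 18 to June 1 is (31 − 18) + 1 = 14 days elapsed, or 14 + 1 = 15 dates with both ends counted. The Sample section states 15, so it counts inclusively, as the example does.

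**Step 3: compare the two windows.**

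| Email date | Inclusive close | Literal close |
|---|---|---|
| 5/20/20, one week | 5/26/20 | 5/27/20 |
| 6/1/20 (last email date), one week | 6/7/20 | 6/8/20 |
| 5/20/20, 31 days | 6/19/20 | 6/20/20 |

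Both one-week windows, measured from the email date, contain 5/20. A same-day enrolment is therefore counted under either close, and moving the cutoff to 5/27 would remove none. Same-day noise is not a consequence of this discrepancy. By calendar date, 5/20 to 5/27 is eight dates, so the literal close is no more obviously a week than the example's.

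**Step 4: how much could one day move the result?** The documents give no daily enrolment counts, so everything here is assumption.
- If enrolments were uniform over 5/20 to 5/27, the disputed date would hold 1/8 = 12.5% of them. With clustering soon after the email the share falls toward 0.
- Suppose a fraction f of events is lost equally in both groups. The risk ratio is then unchanged: p₁(1 − f) / [p₀(1 − f)] = p₁/p₀.
- The odds ratio barely moves. Take assumed risks of 0.075 (email) and 0.05 (control). The odds ratio is (0.075/0.925)/(0.05/0.95) = 1.541. With f = 0.125 the risks become 0.065625 and 0.04375, and the odds ratio is (0.065625/0.934375)/(0.04375/0.95625) = 1.535.
- For uncommon events the standard error of the log odds ratio varies roughly as 1/√events, so it would rise by about 1/√0.875 = 1.069, or 7%, at f = 0.125.

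If the email acts early, late enrolments are mostly background and controls lose the larger fraction of their events. Dropping the last day would then move the ratio slightly away from 1. The direction of any change cannot be fixed from the documents.

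**The case for a change.** The strongest case for acting is that the rule, in ordinary usage, excludes the day of the event: seven days after a date is the same weekday a week later. Counting the length of an email period is a different exercise from counting days after an email, so the 15-day figure supports the inclusive reading without proving it. The boundary belongs to the primary endpoint, and one sentence would settle it. With no dated example for 31 days, a reader also cannot confirm that both windows use one convention.

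The wording point stands: the email date is never labelled day 0 or day 1. The inference that the primary result is insecure does not. The example gives a concrete date and reports what was assessed, which is better evidence of the coding than a general phrase that fits either count. The 31-day text contains nothing that conflicts with itself, and one date in 32 (about 3% under the same even-spread assumption) is trivial for a secondary analysis. The claim that event counts differ in every arm needs at least one enrolment on the disputed day in each arm, which nobody can know from these documents.

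**Conclusion.** No change to the plan is needed. The rule and the example agree once the email date is counted as day 1, and that is how the protocol counts its own email period. An analyst would take the cutoff from the dated example and apply it to all three arms.

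Either count yields a sound one-week comparison. The window is anchored to the actual or would-be email date and has the same length in every randomised group, so one day more or less favours neither side. Choosing between them is a matter of convention, with no shown gain in bias, precision or conclusion.

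The discrepancy is one calendar day. Its share of one-week events runs from near zero, if enrolment is prompt, to 12.5% if enrolment is uniform over eight dates. The second figure is an illustration under that assumption and not a measured bound. The verdict rests on the control window being applied as written and on the same count being used in all arms. The pre-registration, which could not be consulted, may already state the convention.

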## Statistical Analysis Plan

The primary question of interest was whether a timely email improves one-week patient portal enrollment when compared with no such email. This was evaluated using a logistic regression (a generalized linear model with a binary distribution and log-link function) in an intent-to-treat design: patients who were randomized to receive an email but whose addresses were scrubbed by the email delivery software were still included in any such comparisons with the control group, so the total sample size was  $N = 5,099$ .

A secondary question of interest was whether one email version performed better than the other. This question was assessed by examining whether a patient opened the email, clicked on the registration link in the email, unsubscribed from email communications, or enrolled within the outcome timeframe (1 week). This was evaluated for all four outcome measures using a logistic regression (a generalized linear model with a binary distribution and log-link function). These analyses focused on patients' responses to the two email conditions and thus only included patients who were successfully sent the email,  $N = 2,075$ . Unsubscribe data was unexpectedly unavailable at 1-week post-intervention, so this measure was collected and analyzed at 1-month post-intervention instead.

Finally, for the primary question of interest, a secondary analysis was conducted 1 month (31 days) after the intervention.

For all tests, odds ratios (ORs) were calculated, along with 95% confidence intervals (CIs); two-tailed p-values  $< 0.05$  were used to determine statistical significance.

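### Do four unadjusted tests of the two email versions, with no lead outcome named, call for a change to the plan?

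*Combined protocol and SAP*

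**What the plan says.** The Purpose section ties the main aim, email against no email, to portal enrollment. For the other aim it says only: "Secondly, this study A/B tested 2 different versions of the timely email". The second paragraph of the Statistical Analysis Plan restates that aim as "A secondary question of interest was whether one email version performed better than the other". It is assessed by "whether a patient opened the email, clicked on the registration link in the email, unsubscribed from email communications, or enrolled within the outcome timeframe", with a separate logistic regression for each of the four.

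Three outcomes keep the one-week window. Unsubscribe data could not be had at one week, so "this measure was collected and analyzed at 1-month post-intervention instead".

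The last paragraph sets one criterion for everything: "For all tests, odds ratios (ORs) were calculated, along with 95% confidence intervals (CIs); two-tailed p-values" below 0.05 "were used to determine statistical significance". Neither the Study Protocol nor the Statistical Analysis Plan gives a family-wise error rate, a ranking of the four outcomes, or a rule for calling one version the winner. For interventions and outcome measures the Study Protocol refers to a pre-registration, which is not part of this document and may rank the outcomes.

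**The concern.** Asking which version performed better invites a single verdict, yet four tests can deliver it. The primary question names its outcome (one-week enrollment); this one does not.

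The four outcomes also do not point the same way. Opening, clicking and enrolling are favourable, while unsubscribing is unfavourable and is measured over a longer window. A version could gain on opens and lose on unsubscribes, and the document does not say what would then be concluded.

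If a reader or author accepted any one significant result as proof of a better version, chance differences would be taken for real ones more often than the 0.05 criterion suggests. At stake is the choice of email version for future use, not whether emailing works.

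**Working it through.** **Inputs from the document.** There are four outcomes, each tested at a two-tailed 0.05 (Statistical Analysis Plan). The number of delivered emails is 2,750 in the Sample section, which its own counts reproduce: 3,340 − 404 − 186 = 2,750. The Statistical Analysis Plan gives 2,075 for the same comparison. That mismatch is a separate point, so both are carried: 2,750/2 = 1,375 per version, and 2,075/2 = 1,037 rounded down, assuming an equal split. There is no stated family-wise rate to reproduce.

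**Assumed.** The document gives no outcome rates and no correlations, so every figure below except the independent and perfectly correlated cases rests on assumptions.

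**1. Independent tests, identical versions.** P(at least one p < 0.05) = 1 − (1 − 0.05)⁴ = 1 − 0.8145 = 0.185. The ceiling under any dependence is 4 × 0.05 = 0.20.

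**2. Equally correlated tests** (simulated z-statistics):

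| Correlation | 0.3 | 0.5 | 0.7 | 0.9 | 0.95 | 1.0 |
|---|---|---|---|---|---|---|
| Any of four | 17.4% | 15.5% | 13.0% | 9.3% | 8.0% | 5.0% |

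**3. Clicks nested within opens, no true difference** (pooled z-tests). The rate sets are (open, click given open, enrol given click, enrol given no click, unsubscribe given open). The last column is a different case: one version truly raises opens by 5 points, later steps are unchanged, and opens is significant while enrollment is not.

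| Assumed rates | Any of four, 1,375 per version | Any of four, 1,037 per version | True rise in opens: opens significant, enrollment not (1,375) |
|---|---|---|---|
| .4, .2, .6, .03, .02 | 17.5% | 17.3% | 69% |
| .5, .4, .7, .02, .01 | 15.8% | 15.7% | 60% |
| .3, .1, .5, .05, .03 | 18.2% | 18.0% | 75% |
| .4, .5, .8, .005, .002 | 12.3% | 11.7% | 50% |
| .5, .8, .9, .005, .002 | 11.6% | 10.8% | 28% |
| .4, .9, .95, .002, .02 | 12.6% | 12.4% | 14% |
| .4, .95, .97, .001, .003 | 10.3% | 9.3% | 9% |
| .2, .1, .3, .01, .005 | 16.1% | 15.2% | 83% |

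Ten further assumed rate sets, tested with Wald log-odds-ratio tests, gave 7.4–15.9% at 2,750 delivered and 7.4–15.0% at 2,075. The values of 7–8% arise when nearly every opener clicks and nearly every clicker enrolls. So 9% is not a floor.

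**4. What adjustment would buy and cost.** Bonferroni at 0.05/4 = 0.0125 gives 1 − (1 − 0.0125)⁴ = 4.9% under independence. To detect 40% against 45% opened at 1,375 per version, the standard error is √(2 × 0.425 × 0.575/1,375) = 0.01885, so the expected z is 0.05/0.01885 = 2.65. Power is about Φ(2.65 − 1.96) = 76% at 0.05 and Φ(2.65 − 2.50) = 56% at 0.0125, which is also Holm's first step.

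**5. Against which rule?** The percentages in steps 1 to 3 for any of four are the error of declaring a winner on any one significant outcome. The Statistical Analysis Plan contains no such rule. It calculates an odds ratio with an interval for each outcome and judges each on its own test. On that reading the nominal error for opens is 5%, for clicks 5%, and so on, as declared.

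**The case for a change.** The best case for acting is that the text is silent where a verdict is implied, that the inflation is real under a reading nobody has ruled out, and that one or two sentences would remove the ambiguity without new data or loss of power. The silence is real and the arithmetic is right.

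Less stands on necessity. Most of what those sentences would ask for is already in the Statistical Analysis Plan: the comparison is called secondary, all four outcomes are analysed, and effect sizes with intervals are calculated for every test. What is left is the word unadjusted, the habit of naming the outcome when a version is called better, and a citation if the pre-registration ranks the outcomes. None of these changes an estimate, an interval or a p-value. Holm-adjusted values alongside would be harmless, but whether to adjust labelled secondary outcomes is a choice on which reasonable statisticians differ.

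It can also be argued that the outcomes will often disagree, as the last column of the table suggests. The range there, 9–83% at 1,375 per version (9–73% at 1,037), is too wide to support any particular size. Nor is it a conflict in direction. In that scenario the opens result is a true positive and enrollment truly rises a little too; its test simply has less power. That is not a multiplicity error.

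Finally, the document is written in the past tense and reports delivered counts and the loss of the one-week unsubscribe data. Naming a lead outcome now, unless it was documented before the results were known, would be a post hoc choice and could do more harm than the gap it closes.

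**Conclusion.** No change to the plan follows. The document leaves a gap: four secondary tests, no lead outcome and no combining rule. But it breaches no error rate that it states, and the primary comparison is unaffected. The inflation is 18.5% for independent tests, about 7–18% under the assumed rates and 5% at perfect correlation. It arises only if someone adopts an any-one-is-enough rule that the Statistical Analysis Plan does not contain. Analysts fill such a gap in the ordinary way, by presenting all four odds ratios with their intervals as unadjusted secondary results and saying on which outcome a version did better.

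This rests on the results being reported outcome by outcome. A report that declared an overall winner from one of the four, without saying so, would deserve criticism, but as a fault of that report.

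### Unsubscribes are analysed by ordinary logistic regression with no sparse-data method; if they are rare (about 0.2% or lower, an assumption), Firth-penalised regression would be a cheap improvement

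*Combined protocol and SAP*

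**What the plan says.** The Statistical Analysis Plan (second paragraph) asks whether one email version did better than the other on four binary measures. Unsubscribing is one of them: "unsubscribed from email communications, or enrolled within the outcome timeframe (1 week". A single method serves all four: "This was evaluated for all four outcome measures using a logistic regression".

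The closing paragraph promises the same summary throughout: "For all tests, odds ratios (ORs) were calculated, along with 95% confidence intervals (CIs". Two-tailed p-values below 0.05 "were used to determine statistical significance". The plan does not say whether the p-values and intervals are Wald or likelihood-ratio, and it names no exact, penalised or other method for small counts.

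Unsubscribes were measured over a month because "Unsubscribe data was unexpectedly unavailable at 1-week post-intervention". The documents give no unsubscribe count, expected rate, target difference or power for this comparison.

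On the denominator, the Sample section starts from 3,340 patients allocated to an email and ends "leaving a total of N = 2,750 emails delivered". The Statistical Analysis Plan gives 2,075 for the same comparison.

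**The concern.** Unsubscribing after a single email could be much rarer than opening it or clicking in it. A model that suits common outcomes can fail on a handful of events in two ways.

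- If either version has no unsubscribes, the maximum-likelihood OR is zero, infinite or undefined, and the promised OR and CI cannot be reported.
- With a few events in each version, the large-sample tests no longer hold their nominal 5% level. The Wald test becomes far too conservative and the ordinary likelihood-ratio test too liberal, so the same counts can give opposite conclusions depending on which one the software prints.

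At stake is how one of the four version comparisons is read. The primary question, email against no email, is not affected.

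**Working it through.** **Denominator.** From the Sample section: 3,340 − 404 invalid addresses − 186 bounced = 2,750. This agrees with that section and not with the 2,075 in the Statistical Analysis Plan. I use 2,750 and show the effect of 2,075.

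**Assumptions.** An equal split, 2,750 / 2 = 1,375 per version, because the documents do not state the ratio. Unsubscribe rates from 0.1% to 1%, because none is given.

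**Chance that at least one version has no events**, with the same rate r in both: 1 − (1 − (1 − r)^1375)².

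- r = 0.1%: 0.999^1375 = 0.253; 1 − 0.747² = 44%
- r = 0.2%: 0.998^1375 = 0.064; 1 − 0.936² = 12%
- r = 0.5%: 0.995^1375 = 0.0010; 1 − 0.999² = 0.2%
- r = 1%: effectively zero

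With 2,075 in place of 2,750 (about 1,037 per version), the first three become 58%, 24% and 1.1%.

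**True level at nominal two-sided 5%.** For every pair of counts (a, b), weight by Binomial(1375, r) × Binomial(1375, r) and add up the weights of the pairs with p < 0.05. A zero count is treated as non-significant under Wald.

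| Rate | Expected events per version | Wald | Likelihood ratio | Firth, penalised likelihood |
|---|---|---|---|---|
| 0.1% | 1.4 | 0.01% | 8.3% | 0.7% |
| 0.2% | 2.8 | 0.3% | 9.1% | 2.7% |
| 0.5% | 6.9 | 3.1% | 6.1% | 4.4% |
| 1% | 13.8 | 4.3% | 5.2% | 4.6% |

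**One illustrative result: 0 vs 6 unsubscribes.** The Wald p-value is close to 1 and there is no finite OR. The likelihood-ratio p-value is 0.004, Fisher's exact p-value is 0.031 and the Firth penalised-likelihood p-value is 0.013. With two groups, the Firth OR equals the OR after adding one-half to each cell: (6.5 × 1375.5) / (0.5 × 1369.5) = 13.1.

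**Power, by the same enumeration with different rates in the two versions.**

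| Rates | Wald | Fisher | Firth, penalised likelihood |
|---|---|---|---|
| 0.1% vs 0.5% | 18% | 35% | 46% |
| 0.2% vs 0.6% | 24% | 27% | 36% |
| 0.1% vs 0.2% | 0.3% | 1.8% | 4.6% |
| 0.2% vs 0.4% | 5% | 8% | 13% |
| 0.5% vs 1% | 30% | 25% | 31% |
| 1% vs 2% | 58% | 52% | 58% |

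The ordinary likelihood-ratio test rejects more often (16.5% at 0.1% vs 0.2%), but its level there is above 5%, so its power is not comparable. The gain with Firth depends on using the penalised likelihood for the test. Adding one-half to each cell and then applying a Wald test gives a finite OR but only 0.3% power at 0.1% vs 0.2%.

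**The case against.** The strongest reply is that the premise is not in the documents. No unsubscribe rate appears, the serious figures need about 0.2% or lower, and measuring over a month rather than a week can only add events. That stands: the point is conditional.

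Second, the plan never names the Wald test. A reader might infer that the planned analysis cannot detect a lopsided count, but 0 vs 6 gives p = 0.004 by the likelihood-ratio test, which is also ordinary logistic regression. This stands against that inference. It does not make the likelihood-ratio test a sound remedy, given its level of 8% to 9%, and it shows that the choice left open matters.

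Third, a reader might infer that logistic regression is why a real difference would be missed. For a doubling at low rates that is wrong. Power is low by every valid method because events are few: Firth reaches only 4.6% at 0.1% vs 0.2%. The method makes a material difference only for more lopsided sparse counts.

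Fourth, unsubscribing could be taken as the trial's only harm measure, to be weighed against benefit. The documents describe no harm objective and no such weighing. They list it as one of four measures of which version performed better.

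Finally, a zero count is conspicuous, and a zero count with a Fisher-significant split is unlikely: 1.6% at 0.1% vs 0.2% and 3.0% at 0.2% vs 0.4%. That is fair, but the plan still does not say what the analyst then reports, and the Wald level is also distorted when neither version has a zero.

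**Conclusion.** The concern holds in a narrow, conditional form. The plan promises an OR and CI for unsubscribes from a model that may not supply them when events are very few, and it leaves open a choice of test that then matters. At 0.1% to 0.2% the chance of no finite OR is 44% to 12%, and neither ordinary test is near its nominal level. At 0.5% the distortion is small, and at 1% it is essentially gone. All of this rests on the assumed rates and equal split. The smaller denominator of 2,075 would make the zero-event risk somewhat worse.

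The documents do not support saying that the analysis has almost no power in general: at 1% vs 2% ordinary logistic regression has 58%, and at 2% vs 4% it has 87%. Whatever the method, with few events a non-significant unsubscribe comparison should not be read as no difference between versions. I would class the change as an optional, cheap improvement to a secondary analysis.

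**What to change.** For the unsubscribe outcome only, use Firth-penalised logistic regression, reporting the penalised profile-likelihood 95% CI and p-value, and show the raw counts and denominators by version. Ordinary logistic regression can stay for opens, clicks and enrolment. Fisher's exact test with an exact CI would also cope with a zero count, but it has less power than Firth in every scenario above, and less than Wald from 0.5% vs 1% upward.

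Three clarifications belong with it:

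- State whether the other tests and intervals are Wald or likelihood-ratio.
- Reconcile the 2,075 with the 2,750.
- Correct the description "a generalized linear model with a binary distribution and log-link function", since ORs come from a logit link.

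The cost is one sentence in the plan and a standard software option. The plan is written in the past tense and the data are in hand, so this would be a short re-analysis, labelled as added afterwards. The statistical downside is slight shrinkage of the OR. No power is lost when events are plentiful (58% for both methods at 1% vs 2%).

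### One-week enrolment is compared between email versions only in the 2,750 patients whose email was delivered, leaving out 590 of the 3,340 randomised (17.7%) whose enrolment is also known

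*Combined protocol and SAP*

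**What the plan says.** The Sample section of the protocol states that "3,340 patients were allocated to an email condition". It then counts 404 patients whose addresses the delivery software rejected before sending, after which "an additional 186 emails bounced, leaving a total of N = 2,750 emails delivered". The same section makes that delivered total the basis for every comparison between the two email conditions.

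The Statistical Analysis Plan repeats the rule for its secondary question. It lists four outcomes (opening, clicking, unsubscribing and one-week enrolment), gives one logistic model for all of them, explains that the focus is on how patients responded to the two emails, and says the analyses "thus only included patients who were successfully sent the email". The sample size printed in that sentence is 2,075.

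On where enrolment comes from, the Sample section says that health records "for study patients were subsequently examined to evaluate portal enrollment". Three of the 5,012 randomised patients had no record left. They were removed before the 3,340 was counted, leaving 5,009. On email versus control, the section says of the 5,009: "All comparisons between patients emailed and those not contacted were conducted within this total". The SAP calls this comparison intent-to-treat and keeps patients whose addresses were scrubbed.

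**The concern.** A single delivered-only population serves four outcomes of two kinds. Opening, clicking and unsubscribing do not exist without a received email, so limiting them to delivered emails is sound. Enrolment exists for everyone with a health record, and every one of the 3,340 has one.

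The same outcome, over the same week, is therefore analysed as randomised against control but by delivery status between versions. Delivery is determined after allocation. The pre-send flags are unlikely to depend on which version was assigned. The bounces came after a version had been sent and could in principle depend on it. The documents give neither count by version, so balance cannot be checked.

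Two things are at stake. One is interpretation: the odds ratio answers which version works better among people it reaches, and the plan offers no estimate of which works better among people it is assigned to. The other is the protection of randomisation, which is given up for an outcome where it could be kept at almost no cost.

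**Working it through.** **1. Reproduce the plan's count** (inputs from the Sample section)

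- Allocated to an email: 3,340. Flagged: 404. Bounced: 186.
- 3,340 − 404 − 186 = 2,750, which matches the Sample section exactly.
- The SAP's 2,075 does not match: 2,750 − 2,075 = 675. If 2,075 were the number really used, 3,340 − 2,075 = 1,265 patients (37.9%) would be missing.

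**2. Size of the exclusion**

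- Flagged: 404/3,340 = 12.1%.
- Bounced: 186/3,340 = 5.6%. As a share of those sent, 186/(3,340 − 404) = 186/2,936 = 6.3%.
- Total: 590/3,340 = 17.7%.

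**3. How far unequal bouncing could move the delivered-only odds ratio**

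The documents give no enrolment rates and no split by version, so the following are assumptions: 1,468 sent per version (2,936/2), no true difference, and 10% enrolment. Let *x* and *y* be the bounces in versions A and B, with *x* + *y* = 186 and *y* > *x*. The extra bounced patients in B would have enrolled at *m* times the 10% rate, with *m* = 0 or 2.

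- A: delivered 1,468 − *x*; enrolled 0.10(1,468 − *x*).
- B: delivered 1,468 − *y*; enrolled 0.10(1,468 − *x*) − 0.10*m*(*y* − *x*).
- Odds ratio is B to A. The interval is exp(log OR ± 1.96 SE), with SE the root of the summed reciprocals of the four cells.

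| Bounces A/B | Test of the split itself | *m* | Enrolled/delivered A | Enrolled/delivered B | OR (95% CI) | p |
|---|---|---|---|---|---|---|
| 79/107 | z = 2.12, p = 0.034 | 0 | 138.9/1,389 = 10.0% | 138.9/1,361 = 10.21% | 1.023 (0.798 to 1.311) | 0.86 |
| 79/107 | as above | 2 | 138.9/1,389 = 10.0% | 133.3/1,361 = 9.79% | 0.977 (0.761 to 1.255) | 0.86 |
| 60/126 | z = 5.00, p = 5.7 × 10⁻⁷ | 0 | 140.8/1,408 = 10.0% | 140.8/1,342 = 10.49% | 1.055 (0.824 to 1.350) | 0.67 |
| 60/126 | as above | 2 | 140.8/1,408 = 10.0% | 127.6/1,342 = 9.51% | 0.946 (0.735 to 1.217) | 0.66 |

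The first split is already unusual by chance. The second is an outer bound.

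**4. What the as-randomised comparison would cost in power**

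Assume 1,670 allocated per version, of whom 1,375 delivered and 295 not, with enrolment of 10% and 13% among the delivered. Power is for a two-sided 5% test of two proportions (normal approximation).

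| Population | Rates | Difference (points) | OR (95% CI) | Power |
|---|---|---|---|---|
| Delivered, 1,375 per version | 10.0% v 13.0% | 3.0 | 1.345 (1.062 to 1.703) | 69% |
| All 1,670, undelivered enrol at 0% | 8.23% v 10.70% | 2.47 | 1.336 (1.058 to 1.687) | 68% |
| All 1,670, undelivered enrol at 10% | 10.0% v 12.47% | 2.47 | 1.282 (1.033 to 1.591) | 62% |

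The difference shrinks by the delivered share, 2,750/3,340 = 0.823: 3.0 × 0.823 = 2.47 points.

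**The case against.** The restriction is declared in both the protocol and the SAP, and the stated reason, that these analyses concern responses to the emails, is offered for all four outcomes. Intent-to-treat is claimed only for comparisons with control. Asking whether emailing helps as randomised, and which version works better among those reached, is a coherent pair of questions. Patients who received neither version cannot show which one is better, and adding them dilutes the contrast. Of the 590 dropped, 404 (68%) were flagged before anything was sent, so only the 186 bounces offer a route to bias. The documents do not describe the versions, so nothing shows that bouncing could differ between them. The trial is already complete, so a new model would be post hoc.

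Much of this stands. The delivered-only analysis is legitimate, bias is not demonstrated, and 17.7% measures how many patients are left out rather than how wrong the answer is. In the assumed example, dilution can move the estimate more than any plausible bounce imbalance would.

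What does not follow is that the as-randomised result should be absent. The stated reason supports analysing recipients. It does not explain why an outcome known for every randomised patient is reported only that way. Reporting both forces no choice between the two questions, and an added analysis labelled post hoc is still informative.

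**Conclusion.** The point holds as a low-severity suggestion. Between versions, enrolment is analysed in 2,750 of the 3,340 patients randomised to an email, although the outcome is known in all of them and the comparison with control uses all of them. The reported odds ratio is an effect among recipients, without its as-randomised counterpart.

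Any distortion is probably small. In the scenarios above, a null odds ratio moves to 0.98 or 1.02 under a bounce imbalance that is itself unusual, and to 0.95 or 1.05 at the outer bound. None of these reaches significance. The figures rest on an assumed even split of emails sent, an assumed 10% enrolment rate and assumed bounce splits. The question is secondary, and the email-versus-control result does not change.

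Separately, the 2,075 printed in the SAP contradicts the 2,750 that the Sample section's own counts produce. It may be a digit transposition, but the documents do not settle it. It has to be resolved whatever view is taken of the analysis population.

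**What to change.** - Add a comparison of one-week enrolment by assigned version in all 3,340 patients, using the same logistic model, and report it beside the delivered-only result. If results have already been seen, label it post hoc.
- Describe the delivered-only enrolment result as an effect among recipients.
- Leave opening, clicking and unsubscribing on the delivered set.
- Give the flagged (404) and bounced (186) counts by version.
- Reconcile 2,075 in the SAP with 2,750 in the Sample section, and confirm which number the analyses used.

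The cost is one model on data already held. Its limitation is dilution: the enrolment difference shrinks by up to about 18% (1 − 0.823), and in the worked example power falls from 69% to between 62% and 68%. The delivered-only result is still reported, so no information is lost.
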